## 9.2 Serious Adverse Events

An adverse event or adverse reaction is considered serious if, in the view of either the Investigator or Sponsor, it results in any of the following outcomes:

- Death;
- A life-threatening adverse event;
  - NOTE: An adverse event or adverse reaction is considered “life-threatening” if, in the view of either the Investigator or Sponsor, its occurrence places the subject at immediate risk of death. It does not include an event that, had it occurred in a more severe form, might have caused death.
- Requires hospitalization or prolongation of existing hospitalizations;
  - NOTE: Any hospital admission with at least 1 overnight stay will be considered an inpatient hospitalization. An emergency room visit without hospital admission will not be recorded as a SAE under this criterion, nor will hospitalization for a procedure scheduled or planned before signing of informed consent. However, unexpected complications and/or prolongation of hospitalization that occur during elective surgery should be recorded as adverse events and assessed for seriousness. Admission to the hospital for social or

situational reasons (i.e., no place to stay, live too far away to come for hospital visits) will not be considered inpatient hospitalizations.

- A persistent or significant disability/incapacity or substantial disruption of the ability to conduct normal life functions;
  - A congenital anomaly/birth defect; or
  - An important medical event.
- NOTE: Important medical events that may not result in death, be life-threatening, or require hospitalization may be considered an SAE when, based upon appropriate medical judgment, they may jeopardize the subject and may require medical or surgical intervention to prevent one of the outcomes listed above. Examples of such medical events include allergic bronchospasm requiring intensive treatment in an emergency room or at home, blood dyscrasias or convulsions that do not result in inpatient hospitalizations, or the development of drug dependency.

### **9.3 Serious Adverse Event Reporting – Procedures for Investigators**

#### **Initial Reports**

Serious adverse events related to a study-specific procedure that occur between the Screening Visit and the Randomization Visit, and all SAEs occurring from the time of randomization until the Day 90 Safety Visit, must be reported to Medpace Clinical Safety within 24 hours of the knowledge of the occurrence (this refers to any adverse event that meets any of the aforementioned serious criteria). All SAEs that the Investigator considers related to study drug occurring after the Day 90 Safety Visit must be reported to the Sponsor.

To report the SAE, complete the SAE form electronically in the electronic data capture (EDC) system for the study. When the form is completed, Medpace Safety personnel will be notified electronically and will retrieve the form.

If the event meets serious criteria and it is not possible to access the EDC system, send an email to Medpace Safety at [[contact]](mailto:[contact]) or call the Medpace SAE hotline (phone number listed below), and fax the completed paper SAE form to Medpace (fax number listed below) within 24 hours of awareness. When the EDC system becomes available, the SAE information must be entered within 24 hours of the system becoming available.

Safety Contact Information: Medpace Clinical Safety

Medpace SAE hotline – USA:

[contact], Dial 3 or [contact], Dial 3

[contact] or [contact]

Email: [[contact]](mailto:[contact])

Medpace SAE hotline – Europe:

[contact]

[contact]

Email: [[contact]](mailto:[contact])

### Follow-Up Reports

The Investigator must continue to follow the subject until the SAE has subsided or until the condition becomes chronic in nature, stabilizes (in the case of persistent impairment), or the subject dies.

Within 24 hours of receipt of follow-up information, the Investigator must update the SAE form electronically in the EDC system for the study and submit any supporting documentation (e.g., subject discharge summary or autopsy reports) to Medpace Clinical Safety via fax or email. If it is not possible to access the EDC system, refer to the procedures outlined above for initial reporting of SAEs.

### **9.4 Pregnancy Reporting**

If the subject or partner of a subject participating in the study becomes pregnant from the time of randomization until the Day 90 Safety Visit, the Investigator should report the pregnancy to Medpace Clinical Safety within 24 hours of being notified. Medpace Clinical Safety will then forward the Exposure In Utero form to the Investigator for completion.

The subject or partner should be followed by the Investigator until completion of the pregnancy. If the pregnancy ends for any reason before the anticipated date, the Investigator should notify Medpace Clinical Safety. At the completion of the pregnancy, the Investigator will document the outcome of the pregnancy. If the outcome of the pregnancy meets the criteria for immediate classification as an SAE (i.e., postpartum complication, spontaneous abortion, stillbirth, neonatal death, or congenital anomaly), the Investigator should follow the procedures for reporting an SAE.

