## **POPULATION:**

### Inclusion Criteria

Subjects must meet all of the following criteria at the Screening and Randomization Visits in order to be eligible for randomization into the study:

1. Subject, legally authorized representative, or council of independent physicians (CIP) (if applicable) has provided written informed consent;
2. Subject is  $\geq 18$  years of age at the time of enrollment;
3. Subject is currently hospitalized and is mechanically ventilated endotracheally (i.e., orotracheal or nasotracheal) and, in the Investigator's opinion, will require ongoing ventilator support for at least 48 hours;

NOTE: Subjects with a tracheostomy at the time of enrollment are not eligible. After enrollment, conversion to tracheostomy is permitted per standard of care.

4. Female subjects must not be pregnant or lactating. Female subjects of childbearing potential must have a documented negative pregnancy test at the Screening Visit. Female subjects may be enrolled on the basis of a negative urine pregnancy test, pending the result of a negative serum pregnancy test prior to randomization; and
5. Female subjects of childbearing potential and non-surgically sterile male subjects who are sexually active must agree to use an approved highly effective form of contraception from the time of informed consent until 165 days post-dose. Approved forms of contraception include hormonal intrauterine devices, hormonal contraceptives (oral birth control pill, depo, patch, or injectable) together with supplementary double barrier methods such as condoms or diaphragms with spermicidal gel or foam.

NOTE: The following categories define women who are NOT considered to be of childbearing potential:

- Premenopausal female with 1 of the following:
    - Documented hysterectomy,
    - Documented bilateral salpingectomy, or
    - Documented bilateral oophorectomy, or
  - Postmenopausal female, defined as having amenorrhea for at least 12 months without an alternative medical cause.
-

---

Exclusion Criteria

Subjects who meet any of the following criteria at the Screening and/or Randomization Visit will be excluded from participation in the study:

1. Subject has received intravenous (IV) immunoglobulin therapy within 4 months prior to the Screening Visit;
2. Subject has a chest X-ray or thoracic computed tomography (CT) scan that is definitive for a diagnosis of pneumonia;
3. Subject demonstrates both of the following:

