Following randomization on Day 1, subjects will receive either a single IV dose of 3600 mg of ASN100 (comprised of separate infusions each of 1800 mg ASN-1 and 1800 mg ASN-2) or matching placebos, per their assigned randomization scheme.

If, as part of routine standard of care, additional respiratory and/or other microbiological specimens are collected for culture during the study, results will be documented within the electronic Case Report Form (eCRF). As fully described within the study laboratory manual, bacterial isolates recovered from these specimens that are deemed pathogens by the Investigator (if retained and available at the study site local microbiology laboratory) will be sent to a central microbiology laboratory for confirmation of pathogen identification (all isolates) and susceptibility testing (*S. aureus* isolates only).

NOTE: Subjects who are heavily colonized and who would have otherwise qualified for randomization, but who are found to have already progressed to pneumonia, may be eligible to enroll in a site-specific pilot treatment sub-study. See [Appendix C](#) for criteria.

Randomized subjects will be monitored daily for the signs and symptoms of pneumonia (see Section 7.4.2 and [Table 1](#)) and other *S. aureus*-associated infections while hospitalized up to Day 21.

All randomized subjects will undergo a study visit on Day 22 (+2 days). A follow-up visit will occur on Day 28 (+2 days) to assess mortality. This visit may be conducted via telephone if the subject is no longer hospitalized.

For subjects who remain hospitalized between Day 40 and Day 90 at the institution where they receive study treatment, a follow-up safety visit will be performed on the day of discharge.

All randomized subjects will return for a Safety Visit on Day 90 ( $\pm 7$  days) (if the subject is unable to return to the site, this visit may be conducted by telephone). Subjects who discontinue the study prior to Day 22 will undergo an Early Termination Visit. The end of the study will occur upon completion of the last Day 90 visit by the last subject.

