## 4 SELECTION AND WITHDRAWAL OF SUBJECTS

### 4.1 Inclusion Criteria

Subjects must meet all of the following criteria at the Screening and Randomization Visits in order to be eligible for randomization into the study:

1. Subject, legally authorized representative (LAR), or CIP (if applicable) has provided written informed consent;
2. Subject is  $\geq 18$  years of age at the time of enrollment;
3. Subject is currently hospitalized and is mechanically ventilated endotracheally (i.e., orotracheal or nasotracheal) and, in the Investigator's opinion, will require ongoing ventilator support for at least 48 hours;

NOTE: Subjects with a tracheostomy at the time of enrollment are not eligible. After enrollment, conversion to tracheostomy is permitted per standard of care.

4. Female subjects must not be pregnant or lactating. Female subjects of childbearing potential must have a documented negative pregnancy test at the Screening Visit. Female subjects may be enrolled on the basis of a negative urine pregnancy test, pending the result of a negative serum pregnancy test prior to randomization; and
5. Female subjects of childbearing potential and non-surgically sterile male subjects who are sexually active must agree to use an approved highly effective form of contraception from the time of informed consent until 165 days post-dose. Approved forms of contraception include hormonal intrauterine devices, hormonal contraceptives (oral birth control pill, depo, patch, or injectable) together with supplementary double barrier methods such as condoms or diaphragms with spermicidal gel or foam.

NOTE: The following categories define women who are NOT considered to be of childbearing potential:

- Premenopausal female with 1 of the following:
  - Documented hysterectomy,
  - Documented bilateral salpingectomy, or
  - Documented bilateral oophorectomy, or
- Postmenopausal female, defined as having amenorrhea for at least 12 months without an alternative medical cause.

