### 6.6.3 Safety Visit (Day 90 [ $\pm 7$ Days])

The following procedures will be performed at the Safety Visit on Day 90 ( $\pm 7$  days). If the subject is unable to return to the site, this visit may be conducted by telephone, with procedures performed as appropriate (i.e., concomitant medications and adverse events collected):

- Perform limited physical examination (to include, at a minimum, a pulmonary examination [including auscultation]);
- Obtain vital sign measurements, including oxygenation status;

- Assess ventilator device status (if applicable);
- Obtain a blood sample for ADAs;
- Perform 12-lead ECG;
- Assess for survival and discharge disposition;
- Obtain a blood sample for PK measurement and assessment of anti-*S. aureus* toxin antibodies;
- Track days on ventilator from randomization;
- Track days in ICU (or other observation area) from randomization;
- Record concomitant medications; and
- Perform adverse event assessment.

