- n. Vital sign measurements will include temperature, systolic and diastolic blood pressure, pulse, respiratory rate, and oxygenation status. Blood pressure and pulse will be assessed via an automated device. Manual techniques are only to be used if an automated device is not available. Oxygenation status will be determined via measurement of arterial blood gas, provided the subject has an arterial line placed. If no arterial line is present, pulse oximetry may be used.
- o. Female subjects of childbearing potential must have a documented negative pregnancy test at the Screening Visit. Female subjects may be enrolled on the basis of a negative urine pregnancy test, pending the result of a negative serum pregnancy test prior to randomization. A pregnancy test will also be performed on Day 22 or ET (if applicable). Additional pregnancy testing may occur throughout the duration of the study, per applicable country requirements.
- p. Blood samples for chemistry, hematology, and coagulation will be obtained on Days 2 (+1 day), 4 ( $\pm 1$  day), and 6 ( $\pm 1$  day) of the Monitoring Period, and twice weekly during Week 2 (Day 8 through Day 14) and/or Week 3 (Day 15 through Day 21) of the Monitoring Period while the subject remains hospitalized.
- q. To be obtained if clinically indicated.
- r. Urinalysis to be obtained on Day 6 ( $\pm 1$  day) of the Monitoring Period only.
- s. Procalcitonin testing to occur on the day of diagnosis of pneumonia, if applicable.
- t. If applicable.
- u. A chest X-ray or thoracic CT scan is to be obtained 1 time at the initial Screening Visit. A chest X-ray or thoracic CT scan obtained as part of standard of care within 24 hours prior to the initial Screening Visit is sufficient provided there are no changes in the subject's clinical status (e.g., no change in ventilation status, secretions, or signs/symptoms that may be suggestive of pneumonia) within the 24 hours following imaging.
- v. A chest X-ray or thoracic CT scan obtained within 24 hours of the Randomization Visit is sufficient, provided there are no changes in the subject's clinical status (e.g., no change in ventilation status, secretions, or signs/symptoms that may be suggestive of pneumonia) since the time of imaging.
- w. A chest X-ray or thoracic CT scan is required during the Monitoring Period for those subjects presenting with signs and symptoms of a respiratory infection such as dyspnea, tachypnea, fever, or cough.

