7.5. Relative Day

The date of the initiation of study drug administration will be considered relative day 1, relative days will be calculated as follows only when the full assessment date is known (i.e., partial dates will have missing relative days):

For days before the initiation of study drug administration:

Relative Day = Date of Assessment – Date of the initiation of study drug administration

For days on or after the initiation of study drug administration:

Relative Day = Date of Assessment – Date of the initiation of study drug administration + 1

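### Pregnancy reporting stops at the Day 90 Safety Visit, although contraception is required until 165 days after dosing

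*Protocol*

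**What the plan says.** Two protocol provisions set different end dates.

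- **Precaution period.** Criterion 5 in section 4.1, repeated in the synopsis, says that women of childbearing potential and sexually active men who are not surgically sterile "must agree to use an approved highly effective form of contraception from the time of informed consent until 165 days post-dose".
- **Reporting period.** Section 9.4 asks the Investigator to report within 24 hours of being notified if a subject or partner "becomes pregnant from the time of randomization until the Day 90 Safety Visit". A reported pregnancy is then followed to completion, and a serious outcome goes through the SAE procedure.

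Four other provisions bear on what happens after Day 90.

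- **Section 9.3:** "All SAEs that the Investigator considers related to study drug occurring after the Day 90 Safety Visit must be reported to the Sponsor".
- **Section 3.2:** "The end of the study will occur upon completion of the last Day 90 visit by the last subject".
- **Section 6.6.3:** the Day 90 procedures include no pregnancy test and no question or instruction about pregnancy. If the subject cannot return, "this visit may be conducted by telephone, with procedures performed as appropriate (i.e., concomitant medications and adverse events collected").
- **Appendix A, footnote o:** "A pregnancy test will also be performed on Day 22 or ET (if applicable"). Further testing happens only where a country requires it.

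Neither the protocol nor the SAP extends pregnancy reporting beyond the Day 90 visit, explains why it ends there, or gives a basis for 165 days.

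**The concern.** Section 9.4 uses a form for exposure in utero, so its purpose is to capture possible fetal exposure to study drug. The protocol's own statement of how long that possibility warrants precaution is 165 days. Sites are asked to report and follow pregnancies that begin in only about the first half of that time.

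The practical result is that a later pregnancy could go unrecorded even when the site knows of it. Its outcome would be lost too, because follow-up to completion and the referral of serious pregnancy outcomes both depend on section 9.4 having applied in the first place. What is at stake is completeness of safety information on a new antibody combination. Sample size, type I error and the efficacy analysis are not involved.

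**Working it through.** The documents state no figure for the gap, so there is nothing to reproduce. The check is date arithmetic followed by a reading of the other reporting routes.

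**Inputs**

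- End of contraception: 165 days post-dose (protocol section 4.1, criterion 5).
- End of pregnancy reporting: the Day 90 Safety Visit (section 9.4), with a window of ±7 days, so Day 83 to Day 97 (section 6.6.3).
- Dosing day: Day 1 (protocol section 5.1). SAP section 7.5 uses the same convention: "The date of the initiation of study drug administration will be considered relative day 1".

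**Formula**

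Days post-dose at the visit = visit day - 1. Gap = 165 - (visit day - 1). Share = gap / 165, where the denominator is the post-dose part of the contraception period only.

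| Safety Visit on | Days post-dose | Gap (days) | Share of 165 | Plain count, 165 - visit day |
|---|---|---|---|---|
| Day 83 | 82 | 165 - 82 = 83 | 83/165 = 50% | 82 |
| Day 90 | 89 | 165 - 89 = 76 | 76/165 = 46% | 75 |
| Day 97 | 96 | 165 - 96 = 69 | 69/165 = 42% | 68 |

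The two ways of counting differ by one day, which does not matter here.

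**Does another provision cover those days?**

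Take a conception on Day 100. That is 99 days post-dose, later than the latest permitted visit (Day 97), and 165 - 99 = 66 days before the contraception period ends.

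1. *Section 9.4.* The pregnancy began after the Safety Visit, so there is no duty to report or follow it. By contrast, a pregnancy that began before the visit and came to light afterwards is covered, because the window is defined by when the pregnancy begins.
2. *Section 9.3.* After the Day 90 visit only SAEs considered related to study drug are reportable. An uncomplicated pregnancy is not an SAE under section 9.2. A serious outcome judged unrelated is also outside this route.
3. *Section 9.1.* Adverse events are documented only until the subject's participation is complete, and the last scheduled contact is the Day 90 visit.
4. *Testing and prompts.* The last protocol-wide pregnancy test is at Day 22 or Early Termination, and section 6.6.3 contains no prompt about pregnancy. These concern detection and do not create the gap, but they show that nothing else in the schedule makes up for it.

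With the section 9.4 window ending at 165 days post-dose (Day 166), the gap in the duty falls from 76 days to 0.

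**The case against.** The strongest reply is that Day 90 is a consistent boundary and not a slip confined to section 9.4. Reporting of all SAEs stops there, the ban on immunoglobulin preparations runs to there, and the study ends there. A contraception period says what subjects should avoid. A reporting period says what sites collect. Nothing in the documents says the two must match. It is fair to call this a design choice, but it does not explain why a site told of a pregnancy within the precaution period should have no duty to report it.

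Other points on that side:

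- **No demonstrated hazard.** The basis for 165 days may sit in the Investigator's Brochure, which is not available here. Section 1.3 says the targets are bacterial and reports no cross-reactivity with human tissue. This stands: the point rests on the protocol's own precaution and not on shown fetal exposure or risk.
- **Partial safety net.** A congenital anomaly is an SAE, and one judged related is reportable after Day 90 with no end date. This stands, and it narrows the hole to uncomplicated pregnancies and serious outcomes judged unrelated.
- **Small numbers.** Half of subjects receive placebo, criterion 5 applies to only some of them, and all were ventilated ICU patients. This stands and limits the importance.
- **Instructions to subjects may exist elsewhere.** The consent pages are not in the file, so an instruction to notify the site may be there. This stands as to what subjects are told. It does not change what section 9.4 asks of the Investigator.
- **Wording.** Section 9.4 says the Investigator should report, where section 9.3 says must. The length of the window is the same either way.

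**Conclusion.** The concern holds. Followed as written, the protocol leaves 76 of the 165 post-dose precaution days (46%; 69 to 83 days, or 42% to 50%, over the visit window) with no duty to report or follow a pregnancy that begins then. The only remaining route is a related SAE under section 9.3.

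This rests on counting the dosing day as Day 1 and on reading section 9.4 as governed by when the pregnancy begins, which is what its wording says. The percentages describe calendar time and should not be read as a share of expected pregnancies or of drug exposure. The matter is minor: an inconsistency in safety reporting that is cheap to correct and has no bearing on the primary conclusion.

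**What to change.** - In section 9.4, move the end of the window from the Day 90 Safety Visit to 165 days post-dose. Keep the start at randomization, the 24-hour reporting time from notification and the follow-up to completion.
- In section 6.6.3, add an instruction for the Day 90 visit or call: subjects should notify the site of any pregnancy, in themselves or a partner, that begins up to 165 days post-dose.
- Leave the contraception period at 165 days. Shortening it would make the two dates agree by removing the precaution.

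The cost is protocol wording and one instruction at an existing contact, with no added visit, test or sample. Sites would carry a small duty to report on awareness after the last visit, a mechanism section 9.3 already uses for related SAEs. Capture would remain incomplete because no contact is scheduled after Day 90.
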